10.3 Treatment Assignment Procedures

10.3.1 Group Assignment Procedures

Prior to version 3.0 of the protocol, subjects 18-60 years old were randomized in a 1:1 ratio to Groups 1 and 3A. After protocol version 3.0, no random assignment to groups is planned or will be conducted. As of the writing of protocol version 5.0, Groups 1, 3A, 3B and 4 will not enroll any additional subjects, and no further enrollments are planned for Stage 1. After protocol version 9.0 was implemented, it was decided Groups 7A, 7B, 8A and 8B in Stage 2 will not be opened to enroll subjects.

Subjects enrolled into Stage 2 may elect not to receive ChAd-S-TCE, in which case the subject will only be considered for enrollment into SAM-S-TCE single or double boosted vaccination groups. Subjects that consent to receiving a ChAd vaccine may enroll into groups that do not provide ChAd vaccine, but enrollment into groups providing a ChAd vaccine will be prioritized.

As of the writing of protocol version 5.0, subjects will be enrolled into the different groups according to 1) age (see [Table 1](#)), 2) whether the subject consented to ChAd vaccine, and 3) dose escalation dependencies (as specified in [Section 8.1.6](#)). In protocol version 8.0 Stage 2 Groups 7-8 and 10-12 will enroll 8-12 subjects that are vaccinated, with either no prior infection history or evidence of infection at least 4 months previously into A & B subgroups, respectively. Groups 13-15 will allow sample sizes of 7-10 subjects total with no prespecified ratio for infected vs noninfected.

See [Figure 1](#). Stage 1 does not need to be completed prior to enrollment of subjects in Stage 2.

If replacements are needed, each replacement subject will receive the same treatment as the originally enrolled subject.

Treatment allocation schedules will be generated by a statistician at Emmes, the statistical and data coordinating center (SDCC) for this study. Subjects will be registered using a web-based application developed by Emmes.

After informed consent has been obtained and study eligibility has been established at the Screening Visit, subjects will return to the clinical site for their Enrollment Visit, when the first dose of study product will be administered (see [Section 6.2](#)). Group assignment will occur following confirmation of their eligibility and their willingness to participate.

Per ICH guideline E6: GCP, screening records will be kept at the participating site to document the reason why an individual was screened but failed trial entry criteria. The reasons why individuals failed screening will be recorded in the SDCC Advantage *eClinical* (electronic data capture system).

Enrollment of subjects will be done online using the registration module of Advantage *eClinical*. The assignment code will be prepared by statisticians at the SDCC and included in the registration module for this trial. Advantage *eClinical* will assign each subject to a treatment arm after the demographic and eligibility data have been entered into the system.

Instructions for use of the registration module are included in the Advantage *eClinical* User's Guide.

10.3.2 Masking Procedures

Subjects and site staff will be unblinded as to subjects' group assignments in Stage 1 and Stage 2.

10.4 Planned Interim and Early Analyses

Data may be disseminated to public health officials and partners as needed and included in publications and presentations to inform the global scientific community. Early analyses will include safety and immunogenicity as described in [Sections 10.4.1](#) and [10.4.2](#). Further, the protocol team will review data periodically to confirm that no halting rules have been met as described in [Section 8.6.1](#).

Cumulative safety information, study status, and endpoint results may be published, presented at a public forum, or presented as summaries aggregated by study arm at the discretion of the sponsor while the primary study is ongoing. Any ad hoc analyses, jointly developed by the protocol team, SDCC and/or Gritstone bio, Inc. (formerly known as Gritstone Oncology, Inc.), will be executed by the SDCC as needed. None of the interim analyses will include any formal statistical hypothesis testing; therefore, p value adjustment will not be made to any analyses.

10.4.1 Interim Safety Review

Given the need for rapid review and dissemination of study data for public health reasons, AEs and SAEs may be reviewed as necessary outside of DSMB reviews. The DSMB will not need to meet unless halting rules are met, or as requested by the sponsor or PI, and materials will be provided electronically. Documentation of review and any concerns noted will be solicited electronically.

Safety reviews for sentinel halting rules by the protocol team and for dose escalation criteria by the SSC are described in [Sections 8.5.1](#) and [8.1.6](#). Additional safety reviews may be conducted as necessary.

Safety Reviews by the DSMB

Given the frequency and urgency to review data, the DSMB will not need to meet to assess sentinel halting rules or dose escalation criteria unless halting rules are met or as requested by the SSC.

If any of the halting rules listed in [Sections 8.5.1](#) and [8.5.2](#) are met, cumulative safety data from all enrolled subjects will be summarized for DSMB review.

If no halting rules are met, or in addition to unscheduled DSMB reviews, the DSMB will review cumulative AE data as follows:

- After all subjects in Groups 1, 3A, 3B, and 4 have completed Day 8 post first study vaccination visit.

- After all subjects in Groups 1, 3A, 3B and 4 have completed Day 8 post second study vaccination visit.
- After all subjects in Groups 5-7, 9, 10, 11, and 13-15 have completed Day 8 post study vaccination visit.
- After all subjects in Groups 8 and 12 have completed Day 8 post first study vaccination visit.

The DSMB reviews listed above do not have to occur in a sequential manner and may be combined if milestones are reached on dates that are close together.

In addition, the DSMB will meet to review available safety data after all subjects in all groups enrolled in Stages 1 and 2 have completed the visit that occurs 28 days after their last study vaccination.

Ad hoc safety reports may also be prepared for DSMB review as deemed necessary and appropriate by DMID.

Materials for all DSMB reviews will be provided electronically. Documentation of review and any concerns noted will be solicited electronically.

10.4.2 Interim Immunogenicity Review

Interim data review of immunogenicity may be performed to inform public health decisions.

Statistical analyses of secondary immunogenicity endpoints, by vaccine schedule group, may be performed when subjects have completed key immunogenicity visits. Immunogenicity reviews may be shared with the DSMB, as determined by DMID. Immunogenicity reports may be combined with safety reports if projected milestones for reports will occur close enough to each other where, in the opinion of the protocol team, producing one report, as opposed to two separate reports, is more informative regarding the safety of subjects and more beneficial to the overall needs of the protocol team.

Data may be disseminated to public health officials and partners as needed. In addition, subjects will be informed regarding interim aggregate antibody results after the 4-week timepoint after the last study vaccination.

10.5 Final Analysis Plan

This section describes the final study analyses. All safety data from enrolled subjects will be analyzed according to vaccination group for those subjects who received at least one dose of

study vaccine. Group 3A and Group 3B safety and immunogenicity data collected prior to the second study vaccination may be combined for analysis. In the rare instance that a participant receives the wrong treatment at a specific study product administration time, the Statistical Analysis Plan (SAP) will address how to analyze the participant's safety data. The Safety Analysis Population will include all subjects who received at least one dose of study product.

The Clinical Study Report (CSR) will be completed when all primary and secondary safety, clinical, and immunological endpoint data are available. Any available data from the exploratory endpoints may also be included. Additional exploratory endpoint data may be included in an addendum to the CSR, publication of manuscript(s), or other report. The primary analysis of immunogenicity (secondary) endpoints will use the modified intent-to-treat (mITT) analysis population, defined as individuals who received at least one dose of vaccine and contributed both pre- and at least one post-vaccination venous blood sample for immunogenicity testing for which valid results were reported. In the final analysis, protocol deviations will be reviewed to determine which protocol deviations may affect the analysis. The per protocol (PP) population will then be defined – and this includes all subjects in the mITT subset with the following exclusions:

- Data from all available visits for subjects found to be ineligible at baseline.
- Data from all visits subsequent to the protocol deviations that are considered to affect the science.
- Data from any visit that occurs substantially out of window.

Analyses for primary endpoints will be performed using SAS v9.4.

No formal multiple comparison adjustments will be employed for multiple primary or secondary endpoints. However, multiplicity adjustments will be made for certain primary or secondary endpoint assays, as discussed below, when the assay endpoint is viewed as a collection of hypotheses (e.g., testing multiple pseudo-viruses to determine a positive antiviral functional activity response). Unless otherwise noted, 95% confidence intervals will be calculated. Any statistical tests will be 2-sided and will be considered statistically significant if the p-value is below 0.05.

An SAP will be developed by the SDCC and finalized prior to data lock. Unless specified otherwise in the SAP, missing data will not be imputed.

General Approach

Unless otherwise noted in the SAP, continuous variables will be summarized using the following descriptive statistics: n (non-missing sample size), mean, standard deviation, median, maximum and minimum. The frequency and percentages (based on the non-missing sample size) of

observed levels will be reported for all categorical measures. Unless otherwise specified in the SAP, geometric means of relevant continuous endpoints will be computed as Williams means.

Analysis of the Primary Endpoint(s)

Summaries and analysis of safety data will be presented for the Safety Analysis Population.

Solicited reactogenicity signs and symptoms (local and systemic) will be summarized by severity for each day post study vaccination (Days 1-8) and as the maximum severity over all 7 days.

Additionally, solicited AEs will be analyzed by taking the most severe response over the follow-up period, dichotomizing into a binary variable (none versus mild, moderate, or severe) and using standard techniques, such as exact confidence intervals (CI), to summarize the proportion of subjects reporting each symptom, any application site symptom, and any systemic symptom.

Unsolicited non-serious AEs will be collected from the time of first vaccination through 28 days after each study vaccination. Unsolicited AEs will be coded by MedDRA® for Preferred Term and SOC. All SAEs will be collected from the time of first vaccination through the end of the study. SAEs will be described by detailed listings showing the event description,

MedDRA® Preferred Term and SOC, relevant dates (vaccinations and AEs), severity, relatedness, and outcome for each event. Non-serious unsolicited AEs will be summarized as number and percentage of subjects reporting at least one event in each MedDRA® Preferred Term and SOC, cross tabulated by severity and relationship to study product. Additionally, the proportion of subjects and exact 95% CIs of AEs in aggregate and by MedDRA® categories will be computed.

Clinical laboratory data will be summarized as change from baseline and by severity for each visit, and as the maximum over all post study vaccination visits.

Analysis of the Secondary Endpoint(s)

Antibody titers (binding and neutralizing antibody) will be described by group and timepoint using geometric mean titer (GMT) and geometric fold-rise (GMFR), including 95% confidence intervals based on the t-distribution. Undetectable titers will be imputed as one-half of the lower limit of quantitation and the number and proportion of subjects with undetectable titers at each timepoint will be reported. Plots such as reverse cumulative distributions or longitudinal presentations of GMTs will be presented.

Analysis of ICS endpoints will present the percent of cells expressing various cytokines or combinations of cytokines, including 95% confidence intervals, tabularly and graphically by group, peptide pool/stimulant, and timepoint. ELISpot results will be summarized by cytokine,

group, peptide pool/stimulant, and timepoint using summary statistics and 95% confidence intervals.

Baseline Descriptive Statistics

Summaries of demographic variables such as age, sex, ethnicity, and race will be presented by cohort and overall. Summaries of baseline clinical laboratory values will be presented by cohort and overall.

Tabulation of Individual Subject Data

In general, all data will be listed, sorted by cohort and subject, and when appropriate by visit number within subject.

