Design of the Study:	Open-label, dose escalation, non-randomized study of the safety, tolerability, and immunogenicity of investigational ChAd-S and SAM-S SARS-CoV-2 vaccines with or without TCE. Stage 1 will study dose escalation of homologous and heterologous prime-boost vaccination schedules in healthy naïve adult subjects. Stage 2 will study booster vaccination(s) in adult subjects who previously received COVID-19 EUA/licensed vaccines (see Table 1).
Study Phase:	1
Study Population:	Men and non-pregnant women who are in good health and meet all eligibility criteria will be enrolled: 
• Stage 1: 17 subjects, 18-60 yo• Stage 2: up to 118 subjects, ≥ 18 yo Subjects will be enrolled at one of at least 4 distinct US-based Infectious Diseases Clinical Research Consortium (IDCRC) sites into different groups. Subjects' willingness to receive ChAd vaccines will be assessed and documented at the time of informed consent and considered to determine group assignments.
Number of Sites:	At least 4 domestic clinical research sites
Description of Study Product or Intervention:	ChAd expressing spike alone or spike plus TCE (ChAd-S and ChAd-S-TCE) and SAM expressing spike alone or spike plus TCE (SAM-S and SAM-S-TCE):

- ChAd-S, 5×10^{10} viral particles (vp), intramuscular (IM)
- SAM-S, 3 micrograms (μg) and 30 μg , IM
- ChAd-S-TCE, 5×10^{10} vp, 1×10^{11} vp, and 5×10^{11} vp, IM
- SAM-S-TCE, 3 μg , 6 μg , and 10 μg , IM

Study Objectives:**Primary:**

- To assess the safety and tolerability of different doses of ChAd-S or ChAd-S-TCE, and SAM-S or SAM-S-TCE when administered as:
 - prime-boost in healthy naïve adult subjects.
 - First or second boost in healthy adult subjects previously vaccinated with EUA/licensed mRNA or adenoviral-vectored COVID-19 vaccines.

Secondary:

- To assess the humoral and T cell responses to ChAd-S or ChAd-S-TCE, and SAM-S or SAM-S-TCE.

Exploratory:

- To evaluate memory B cell responses to ChAd-S or ChAd-S-TCE, and SAM-S or SAM-S-TCE.
- To evaluate neutralizing antibody responses to the ChAd vector.

Duration of Individual Subject Participation:

12 months after the last study vaccination

Estimated Time to Last Subject/Last Study Day:

Approximately 24 months

Table 1: Treatment Arms

Stage	Study Population	Group	Sample Size	Vaccination(s)	Day of Dosing/ Interval Between Doses (Days)
1*	Naïve (18-60 yo)	1	4	5 x 10 ¹⁰ vp ChAd-S/ 30 µg SAM-S	28
		3A	3	30 µg SAM-S/ 30 µg SAM-S	28

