		3B	7	30 µg SAM-S/ 3 µg SAM-S	84-129
		4	3	10 µg SAM-S-TCE/ 3 µg SAM-S-TCE	84-129
2**	SAM-S-TCE Boosts after EUA/licensed mRNA (Groups 5-7) and Ad26 (Group 8) COVID-19 Vaccines (18-60 yo)	5	10	3 µg SAM-S-TCE	≥112
		6	10	6 µg SAM-S-TCE	≥112
		7A&B [#] ****	8-12	10 µg SAM-S-TCE	≥112
		8A&B [#] ****	8-12	10 µg SAM-S-TCE/ 10 µg SAM-S-TCE***	≥112/ 56***
		9	8	3 µg SAM-S-TCE	≥112
	SAM-S-TCE Boosts after approved/licensed mRNA (Groups 9-11) and Ad26 (Group 12) COVID-19 Vaccines (>60 yo)	10A&B [#]	8-12	6 µg SAM-S-TCE	≥112
		11A&B [#]	8-12	10 µg SAM-S-TCE	≥112
		12A&B [#]	8-12	10 µg SAM-S-TCE/ 10 µg SAM-S-TCE***	≥112/ 56***
		13	7-10	5 x 10 ¹⁰ vp ChAd-S-TCE	≥112
	ChAd-S-TCE Boosts after approved/licensed mRNA COVID-19 Vaccines (>60 yo)	14	7-10	1 x 10 ¹¹ vp ChAd-S-TCE	≥112
		15	7-10	5 x 10 ¹¹ vp ChAd-S-TCE	≥112

[figure not shown]
*Were enrolled prior to protocol version 5.0. No further enrollment will occur in Stage 1. Group 1A, as noted in protocol version 4.0, is noted above as Group 1. Groups 1B and 2, as noted in protocol version 4.0, have been eliminated, due to anticipated challenges with enrollment of naïve subjects.

**Will be enrolled under protocol versions 5.0 and later; Stage 2 was redesigned in version 5.0 to focus on subjects previously given primary vaccination series of mRNA or Ad26 COVID-19 vaccines and has now been redesigned to also include those given recommended COVID-19 booster vaccinations. All Stage 2 subjects will receive single or double boosts of SAM-S-TCE or a single boost with ChAd-S-TCE. Groups 5, 6, 8, 9, 10, 12, and 13-15 are dose escalations with 3 sentinels/group (irrespective of subgroup) who will be followed for 72 hours post vaccination. After all 3 sentinels are evaluated for 72 hours and no safety issues are observed, the remainder of the group will be enrolled and followed through Day 8 after study vaccination before dose escalation. Dosing in Groups 7 and 11 (10 µg SAM-S-TCE) will proceed with 3 sentinels/group (irrespective of subgroup) monitored for 7 days post vaccination prior to enrollment of the remainder of the group; enrollment into Group 7 will depend on all safety data from Group 11 generated through 28 days of follow up post-vaccination.

***Will administer the highest tolerable dose as determined by the dose escalations. For the SAM-S-TCE double boosting groups, the interval after the last EUA/licensed COVID-19 vaccination will be ≥ 112 days and the interval between the 2 SAM-S-TCE boosts will be 56 days.

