3.2 Study Objectives and Endpoints

Table 2: Objectives and Endpoints (Outcome Measures)

Objectives	Endpoints (Outcome Measures)
Primary	

 To assess the safety and tolerability of different doses of ChAd-S or ChAd-S-TCE, and SAM-S or SAM-S-TCE when administered as: 
 prime-boost in healthy naïve adult subjects boost in healthy adult subjects previously vaccinated with an EUA/licensed mRNA or adenoviral-vectorized COVID-19 vaccine 	
 Occurrence of solicited local reactogenicity signs and symptoms for 7 days following each study vaccination Occurrence of solicited systemic reactogenicity signs and symptoms for 7 days following each study vaccination Occurrence of unsolicited AEs for 28 days following each study vaccination Change from baseline for clinical safety laboratory parameters 7 days after each study vaccination Occurrence of SAEs and AESIs, including PIMMCs, MAAEs and NOCMCs, throughout the entire study following the first study vaccination
Secondary	

 To assess the humoral immunogenicity of ChAd-S or ChAd-S-TCE, and SAM-S or SAM-S-TCE 	
 Response rate, and magnitude of SARS-CoV-2-specific antibody binding and neutralization titers (including against emergent viral strains, e.g., B.1.1.7) in serum samples will be assessed via a range of assays measuring total Spike-specific IgG (ELISA-based), and function (neutralization, RBD binding, or similar) in serum on the following days:

Objectives	Endpoints (Outcome Measures)
	
For Stage 1, Groups 1 and 3A: Days 1 and 29 post Dose 1; then Days 29, 181, and 366 post Dose 2
 
For Stage 1, Groups 3B and 4: Days 1, 29, 57, and 85-130 post Dose 1; then Days 15, 29, 85, 181, and 366 post Dose 2
 
For Stage 2, Groups 5-7A*, 7B*, 9, 10A, 10B, and 11A, 11B, and 13-15: Days 1, 15, 29, 85, 181, and 366 post study vaccination
 
For Stage 2, Groups 8A*, 8B* and 12A, 12B: Days 1, 15, 29, and 57 post Dose 1; then Days 15, 29, 85, 181, and 366 post Dose 2

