6.3 Planned Study Visits for Groups 1 and 3A

At all clinic visits for Groups 1 and 3A, the following study procedures will be performed:

- Interim medical history, including an assessment for new medical conditions, stability of chronic diseases will be obtained by interview of subjects and any changes since the previous clinic visit, phone call, or other form of contact will be noted.
- All concomitant medications will be recorded on the appropriate DCF.
- Vital signs, including oral temperature, pulse, and BP, will be obtained. Subjects must not eat or drink anything hot or cold within 10 minutes prior to taking oral temperature.
- A targeted physical examination may be performed, if indicated, based on review of interim medical history, by a study clinician licensed to make medical diagnoses and listed on the Form FDA 1572 as the site PI or sub-investigator.

6.3.1 Visits 02 and 03, Days 2 and 4, Telephone, Email, or Text Contact**(Windows: Day 2+1 day and Day 4+2 days post 1st study vaccination)**

- Memory Aids will be reviewed with the subjects via telephone, email, or text for any AEs (solicited injection site and systemic reactions, as well as unsolicited AE), SAEs, AESIs, and concomitant medications. Based on the information collected, subjects may be asked to return to the clinic for an evaluation.

6.3.2 Visit 04, Day 8, Clinic Visit**(Window: Day 8+2 days post 1st study vaccination)**

In addition to the study procedures listed in [Section 6.3](#), the following study procedures will also be performed:

- Memory Aid information will be reviewed with subjects.
- A saliva sample will be collected to check for antibodies.
- Approximately 14 mL of venous blood will be collected for safety labs including WBC, HgB, PLT, ALT, AST, ALP, Cr, CK and T Bili.
- Approximately 24 mL of venous blood will be collected for PBMC and plasma storage for secondary research.
- All AEs/SAEs/AESIs including potentially immune-mediated medical conditions (PIMMCs), medically attended adverse events (MAAEs), and new onset chronic medical conditions (NOCMCs) will be recorded on the appropriate DCF.

6.3.3 Visit 05, Day 29, Clinic Visit, 2nd Study Vaccination (Dose 2)**(Window: Day 29±3 days post 1st study vaccination)**

In addition to the study procedures listed in [Section 6.3](#), the following study procedures will also be performed:

- Eligibility criteria will be reviewed with subjects prior to the second study vaccination to ensure continued eligibility.

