6.4.4 Visit 06, Day 57, Clinic Visit

(Window: Day 57±3 days post 1st study vaccination)

In addition to the study procedures listed in [Section 6.4](#), the following study procedures will also be performed:

- Approximately 80 mL of venous blood will be collected for cellular immunology assays.
- Approximately 20 mL of venous blood will be collected for antibody assays.
- Approximately 32mL of venous blood will be collected for PBMC and plasma storage for secondary research.
- All AEs/SAEs/AESIs including PIMMCs/MAAEs/NOCMCs will be recorded on the appropriate DCF.

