6.4.5 Visit 07, Day 85, Clinic Visit, 2nd Study Vaccination (Dose 2)

(Window: Day 85+45 days post 1st study vaccination)

In addition to the study procedures listed in [Section 6.4](#), the following study procedures will also be performed:

- Eligibility criteria will be reviewed with subjects prior to the second study vaccination to ensure continued eligibility.
- A urine or serum pregnancy test will be performed locally by the site within 24 hours prior to the second study vaccination for all women of childbearing potential. Results must be negative and known prior to the second study vaccination.
- Nasal swab will be collected for SARS-CoV-2 PCR prior to the second vaccination.
- Approximately 2 mL of venous blood will be collected for SARS-CoV-2 serology (N-specific).
- Approximately 14 mL of venous blood will be collected immediately prior to the second study vaccination for baseline clinical safety labs (WBC, HgB, PLT, ALT, AST, ALP, T Bili, CK, and Cr) to be performed by the local (clinical) laboratory. The results from these evaluations will not be available or reviewed prior to the second study vaccination.
- Approximately 80 mL of venous blood will be collected immediately prior to the second study vaccination for cellular immunology assays.
- Approximately 20 mL of venous blood will be collected immediately prior to the second study vaccination for antibody assays.
- Approximately 32 mL of venous blood will be collected for PBMC and plasma storage for secondary research.
- Approximately 2.5 mL of venous blood will be collected for identification of transcriptomal signatures associated with vaccine reactogenicity and immunogenicity.
- Approximately 4 mL of blood will be collected for cytokines.
- Subjects will then receive one- 0.25 or 0.5 mL dose of study vaccine (depending on treatment assignment) via a single IM injection into the deltoid muscle. If possible, administer study vaccine in the opposite arm used for the first study vaccination. The site of injection (right or left arm) and time of study vaccine administration to the subject will be recorded on the appropriate DCF. Subjects will be observed in the clinic for at least 45 minutes after the second study vaccination. The second study vaccination site will be examined, post-administration reactogenicity assessments will be performed, and any

AEs/SAEs/AESIs including PIMMCs/MAAEs/NOCMCs will be recorded on the appropriate DCF prior to discharge from the clinic.

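### Pooling Groups 3A and 3B up to dose 2 mixes a 28-day window with an 84-129-day window for the open-ended safety events (AESIs, including PIMMCs, MAAEs and NOCMCs)

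*Protocol*

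**What the plan says.** Section 10.5 makes analysis by vaccination group the rule and then adds an option: "Group 3A and Group 3B safety and immunogenicity data collected prior to the second study vaccination may be combined for analysis". The pool ends at the second dose. No day since dose 1 is given.

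The Table 1 rows are "3A 3 30 µg SAM-S/ 30 µg SAM-S 28" and "3B 7 30 µg SAM-S/ 3 µg SAM-S 84-129": the same first dose, with different intervals to the second. The visit text agrees. For dose 2, Section 6.3.3 (3A) gives "Window: Day 29±3 days post 1st study vaccination" and Section 6.4.5 (3B) gives "Window: Day 85+45 days post 1st study vaccination".

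Table 2 lists five primary safety endpoints. Four have a fixed window after each dose: local and systemic solicited reactions ("Occurrence of solicited local reactogenicity signs and symptoms for 7 days following each study vaccination", with a parallel entry for systemic), safety laboratory change at 7 days, and unsolicited AEs ("Occurrence of unsolicited AEs for 28 days following each study vaccination"). The fifth, SAEs and AESIs including PIMMCs, MAAEs and NOCMCs, runs from dose 1 to the end of the study.

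Two other places collect unsolicited AEs for longer. Section 8.3 follows AEs until 28 days after the last dose. At the 3B Day 57 visit (Section 6.4.4) the instruction is "All AEs/SAEs/AESIs including PIMMCs/MAAEs/NOCMCs will be recorded on the appropriate DCF".

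**The concern.** A boundary set by dose 2 gives equal follow-up only if dose 2 falls at the same time in both groups. Here it does not. For an event class that stays open from dose 1, seven of the ten pooled subjects are watched at least three times as long as the other three. The resulting percentage of subjects with an event refers to no single risk period.

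The affected class accrues with time whether or not the vaccine plays a part. Section 8.1.5 counts any unscheduled medical visit as a MAAE and a confirmed SARS-CoV-2 infection as an AESI, and Stage 1 enrolled naïve subjects. The pool is also the largest set on a 30 µg SAM-S first dose, and Section 10.1 makes preliminary estimation of safety a stated aim. With ten subjects, one late event moves a proportion by 10 percentage points.

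**Working it through.** **Plan's own figure.** The protocol gives no figure for the combined set. The nearest is Table 4 for n=10: 65.1% and 89.3% chance of at least one event at true rates of 10% and 20%. These reproduce: 1 − 0.9^10 = 0.651 and 1 − 0.8^10 = 0.893. They assume one common event rate for all ten subjects.

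**Inputs.** Group sizes 3 and 7, and intervals 28 and 84-129 days (Table 1). The dose-2 visit windows are Day 26-32 for 3A, which is 25-31 days after dose 1, and Day 85-130 for 3B, which is 84-129 days after.

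**Ratio of windows.** 84/28 = 3.0 and 129/28 = 4.6. At the edges of the 3A visit window the range is 84/31 = 2.7 to 129/25 = 5.2.

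**Pooled person-days before dose 2.**
- 3B at 84 days: 3×28 + 7×84 = 672. After day 28: 7×56 = 392, which is 392/672 = 58%.
- 3B at 129 days: 3×28 + 7×129 = 987. After day 28: 7×101 = 707, which is 707/987 = 72%.
- With a common 28-day cut: 10×28 = 280.

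**Effect on a proportion of subjects.** Let q be the 28-day risk of an open-ended event. The protocol gives no value, so q is assumed. With a constant rate, the 3B risk over d days is 1 − (1−q)^(d/28), and the pooled proportion is [3q + 7(1 − (1−q)^(d/28))]/10.

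| Assumed q | 3B risk, d=84 | Pooled | 3B risk, d=129 | Pooled |
|---|---|---|---|---|
| 2% | 5.9% | 4.7% | 8.9% | 6.8% |
| 5% | 14.3% | 11.5% | 21.0% | 16.2% |
| 10% | 27.1% | 22.0% | 38.5% | 29.9% |
| 20% | 48.8% | 40.2% | 64.2% | 51.0% |

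The pooled figure is about 2.0 to 3.4 times the 28-day risk.

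**Which summaries are exposed.**

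| Summary | Window before dose 2, 3A against 3B | Affected by pooling? |
|---|---|---|
| Solicited reactions | 7 days in both | No |
| Day 8 laboratory change | Same visit | No |
| Unsolicited AEs, 28-day endpoint | 28 days in both, up to 3 days less if a 3A subject is dosed early | No |
| Unsolicited AEs, if collected as in Section 8.3 and at the 3B Day 57 visit | About 28 against 84-129 days | Yes |
| SAEs | Shown as listings with dates (10.5) | No |
| AESIs, PIMMCs, MAAEs, NOCMCs, and any aggregate proportion including them | About 28 against 84-129 days | Yes |
| Highest laboratory result over all post-vaccination visits (10.5) | Pre-dose-2 draw at Day 29±3 against Day 85-130 | Yes, if that draw counts |
| Immunogenicity | Summarised by timepoint | No |

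On the last laboratory row, Sections 6.3.3 and 6.4.5 call the pre-dose-2 draw a baseline, so whether it enters the maximum after dose 1 is left open.

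**The case against.** The strongest reply is that most of the dose-1 safety information has equal windows. Four of the five primary safety endpoints are fixed at 7 or 28 days after each dose, and Section 10.5 describes the percentage of subjects with at least one event for non-serious unsolicited AEs, which the endpoint definition stops at 28 days. That stands. A reader might infer that every pooled dose-1 harm rate is distorted; the documents do not support this.

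On unsolicited AEs, the Day 57 instruction can be read as a standard form-completion line that does not redefine the endpoint. That is a fair reading, but it does not settle the matter: Section 8.3 is loose in the same direction, and Sections 6.7 and 6.8 record all AEs in 3B at any early-termination or unscheduled visit before Visit 12. The exposure is real only if this longer collection feeds the table.

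A reader might also infer that the 30 µg SAM-S first dose would look worse than Group 1, whose second dose comes at 28 days. No such comparison is planned, and Section 10.1 rules out hypothesis tests between groups.

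The remaining points concern weight. Pooling is optional, the analysis is descriptive, Stage 1 enrolment is closed, Section 2.2 has already decided against escalation in naïve subjects, and an SAP could set a cut. These keep the point modest. They do not remove it, because the protocol itself names the boundary, and that boundary gives unequal follow-up if applied as written.

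**Conclusion.** The concern holds for a limited set of summaries. If the pooling option is used as worded, proportions for AESIs, PIMMCs, MAAEs and NOCMCs, and aggregate AE proportions that include them, combine windows differing 3.0 to 4.6-fold. The ratio and the 58-72% share of person-time use only the protocol's group sizes and nominal intervals. The pooled proportions of 22-30% and 40-51% also rest on an assumed 28-day risk of 10% or 20% and a constant rate; events that cluster soon after vaccination would be inflated less.

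Unsolicited AEs are affected only if the longer collection is used. The maximum laboratory summary is affected if the pre-dose-2 draw is counted. Solicited reactions, Day 8 laboratory change, listed SAEs and immunogenicity by timepoint need no change.

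**What to change.** 1. In Section 10.5, state that pooled 3A/3B safety summaries cover only events with onset, and laboratory draws taken, from dose 1 through Day 29 and before dose 2.
2. List 3B events with onset after Day 29 and before dose 2 separately, for 3B only.
3. For laboratory values, note that 3B has no safety draw at Day 29 (Section 6.4.3, Table 7), so Day 8 is the only post-dose draw common to both groups within the cut. A pooled maximum should rest on it.
4. Reconcile Section 8.3 and the 3B visit text, including Sections 6.7 and 6.8, with the 28-day unsolicited AE endpoint in Table 2.

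The immunogenicity part of the pooling sentence can stay as it is.

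The cost is a sentence in 10.5, the matching SAP entry and the wording changes in item 4. Onset dates are already recorded (Section 8.1.1), so no data are added. The downside is that later 3B events leave the pooled table and appear only in the 3B listing.
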